### **8.2.2 Success Criteria for Secondary Objectives**

#### **8.2.2.1 Success Criteria for Secondary Immunogenicity Endpoints**

There are no specific success criteria for the assessment of immunoassay results (first secondary objective).

Superiority of aQIV versus aTIV-1 and aTIV-2 for the alternate B strain will be assessed using the GMT ratio ( $GMT_{aTIV}/GMT_{aQIV}$ ) and difference in SCR ( $SCR_{aTIV} - SCR_{aQIV}$ ) at Day 22. Point estimates and two-sided 95% CIs will be obtained as described for the primary endpoint. Superiority will be declared if the upper limit of the two-sided 95% CI for the difference in  $SCR_{aTIV} - SCR_{aQIV}$  is  $< 0\%$ , and the upper limit of the two-sided 95% CI for the GMT ratio ( $GMT_{aTIV}/GMT_{aQIV}$ ) is  $< 1$  for both B strains.

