2.1.2 CO-PRIMARY ENDPOINTS

The immunogenicity of study vaccines will be assessed 21 days (i.e., on Day 22) after vaccine administration by measuring the hemagglutination inhibition (HI) antibody titers to the virus strains included in the vaccines.

The non-inferiority of aQIV compared to aTIV-1, and to aTIV-2 will be assessed for the eight co-primary endpoints of HI geometric mean titer (GMT) and seroconversion rate (SCR) for each virus strain included in the vaccines as follows:

- The GMT ratio* for the A/H1N1 strain;
- The GMT ratio for the A/H3N2 strain;
- The GMT ratio for the B strain (Yamagata lineage);
- The GMT ratio for the B strain (Victoria lineage);
- The difference between the SCR** for the A/H1N1 strain;
- The difference between the SCR for the A/H3N2 strain;
- The difference between the SCR for the B strain (Yamagata lineage);
- The difference between the SCR for the B strain (Victoria lineage).

Immunogenicity results obtained from aTIV-1 and aTIV-2 for both A/H1N1 and A/H3N2 strains will be pooled for comparison with aQIV.

*The GMT ratio is defined as the geometric mean of the post-vaccination (Day 22) HI titer for aTIV-1 (or aTIV-2) over the geometric mean of post-vaccination (Day 22) HI titer for aQIV.

**The SCR is defined as the percentage of subjects with either a pre-vaccination HI titer $< 1:10$ and a post-vaccination HI titer $\geq 1:40$ or a pre-vaccination HI titer $\geq 1:10$ and a ≥ 4 -fold increase in post-vaccination HI titer.

The second co-primary immunogenicity objective for aQIV will be assessed 21 days after vaccine administration by applying CBER criteria for the elderly population for each of the 4 strains included in aQIV. The second co-primary endpoints include:

- The percent of subjects achieving seroconversion (SC) for HI antibody
- The percent of subjects achieving an HI antibody titer $\geq 1:40$

The study is considered successful if all co-primary endpoints are achieved.

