2.2 SECONDARY OBJECTIVES AND ENDPOINTS

2.2.1 SECONDARY IMMUNOGENICITY OBJECTIVES

The secondary objectives of the study are to assess the following, among adults aged ≥ 65 years:

1. To characterize the immunogenicity of aQIV, the aTIV-1 containing the same virus strains as the US licensed adjuvanted trivalent influenza vaccine, and the aTIV-2 containing the alternate B strain, by HI.
2. To demonstrate the immunological superiority of aQIV compared to aTIV-1 and aTIV-2 for the B strain that is not included in each TIV vaccine separately;

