2.4 SUCCESS CRITERIA

The study is considered successful if both co-primary objectives are achieved.

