2.4.2 Success Criteria for Secondary Objectives

2.4.2.1 Success Criteria for Secondary Immunogenicity Endpoints

There are no specific success criteria for the assessment of immunogenicity results (first secondary objective) as the characterization of the immunogenicity of the vaccines are descriptive in nature.

Superiority of aQIV versus aTIV-1 and aTIV-2 for the alternate B strain will be assessed using the GMT ratio ($\text{GMT}_{\text{aTIV}}/\text{GMT}_{\text{aQIV}}$) and difference in SCR ($\text{SCR}_{\text{aTIV}} - \text{SCR}_{\text{aQIV}}$) at Day 22. Point estimates and two-sided 95% CIs will be obtained as described for the primary endpoint. Superiority will be declared if the upper limit of the two-sided 95% CI for the difference in ($\text{SCR}_{\text{aTIV}} - \text{SCR}_{\text{aQIV}}$) is $< 0\%$, and the upper limit of the two-sided 95% CI for the GMT ratio ($\text{GMT}_{\text{aTIV}} / \text{GMT}_{\text{aQIV}}$) is < 1 for both B strains.

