5. SAMPLE SIZE AND POWER CONSIDERATIONS

aQIV will be tested against aTIV comparators. The treatment randomization ratio is 2:1:1 (aQIV: aTIV-1: aTIV-2). This study is powered to achieve 80% power to demonstrate noninferiority over 8 co-primary endpoints, SCRs for 4 strains, GMT for 4 strains using a one-sided alpha of 0.025 for each comparison. No adjustment for multiple endpoints will be made.

For comparisons of SCR a noninferiority margin of 10% (aTIV – aQIV) will be employed. It is assumed that the SCRs for A/ H1N1, A/ H3N2 and B strains for TIV are 73%, 73% and 40% respectively. These estimates are based on the estimated SCR rates of historical data, namely study protocol V70_27. It has been assumed that there is no difference in terms of SCR between aQIV and aTIV for all strains. For comparison of the GMT ratio, a noninferiority of 1.5 (aTIV/aQIV) will be employed. It is assumed that there is no difference between aQIV and aTIV (i.e., a ratio of 1) and that the standard deviation (SD) of log (titer) is 1.2.

Under these assumptions, N FAS = 800 in the aQIV group and 400 in each aTIV group providing 800 and 800 subjects receiving aQIV and aTIV respectively for comparisons of A strains, and 800 and 400 subjects receiving aQIV and aTIV respectively for comparisons of B strains. This provides a total N FAS = 1600. These numbers provide 99.45% power to detect differences in SCR for each A strain and 91.29 % power for each B strain, providing overall 82.42% power for the 4 SCR tests.

For GMT ratio tests each A strain test will have 100% power and each B strain test will have 99.98% power, providing 99.96% power for the 4 GMT ratio tests and consequently 82.39% power for the 8 co-primary endpoints. Overall 1600 FAS subjects will be required. Allowing for a 10% drop-out N=1778 subjects will be recruited.

The immunogenicity was powered to meet the criteria pre-specified in the CBER guidance for acceptable immunogenicity: namely,

- the lower bound of the two-sided 95% confidence interval for the percent of subjects achieving SC should exceed 30%, and
- the lower bound of the two-sided 95% confidence interval for the percent of subject achieving HI antibody titer $\geq 1:40$ should exceed 60%

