8.4 Multiple Comparisons and Multiplicity

No adjustment for multiple comparison and multiplicity will be used.

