11.2.4 Statistical Methods

All statistical analyses for HI titers will be performed on the logarithmically transformed (base 10) values. Individual HI titers below detection limit (<10) will be set to half of that limit (5).

Unadjusted GMTs, GMRs and pertaining two-sided 95% CIs will be calculated assuming log-normal distribution of the titers and will be completed by providing minimum, maximum and median titers for each vaccine group.

Binary data (ie, percentages of subjects with SC and with titer $\geq 1:40$) will be summarized for each group using crude estimates and will be reported together with 2-sided exact 95% CIs. No multiplicity adjustment to the CI levels will be implemented.

For immunogenicity data, it may be reasonable to consider missing immunogenicity values as missing completely at random (MCAR), i.e., not informative. Therefore, the key secondary analysis will comprise a complete case analysis only, without introducing any bias. Imputation methods will not be used.

The following figures will be also produced:

- GMT Reverse Cumulative Distribution Curve – Overall by Strain
- GMT Reverse Cumulative Distribution Curve – by Age Cohort
- GMT Reverse Cumulative Distribution Curve – by Study Treatment

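### The B-strain superiority claim is formal but not conditional on the co-primary objectives, so error across the two claims is uncontrolled; a gate would close this at almost no cost

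*SAP*

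**What the plan says.** **Study success.** SAP 2.4 states: "The study is considered successful if both co-primary objectives are achieved". SAP 2.1.2 applies the same rule to the individual endpoints: "The study is considered successful if all co-primary endpoints are achieved". Protocol 8.1.1.1 counts 16 endpoints: eight for non-inferiority and eight for the CBER criteria.

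**Superiority.** Secondary objective 2 in SAP 2.2.1 is worded as a demonstration: "To demonstrate the immunological superiority of aQIV compared to aTIV-1 and aTIV-2 for the B strain that is not included in each TIV vaccine separately". SAP 11.2.2 and Protocol 8.4.3.3.1 give it null and alternative hypotheses, indexed by aTIV (k = 1, 2). The decision rule in SAP 2.4.2.1 begins "Superiority will be declared if the upper limit of the two-sided 95% CI for the difference in" SCR is below zero. It also requires the upper limit for the GMT ratio to be below 1, and it covers both B strains. The rule is repeated in SAP 11.2.1 and in Protocol 8.2.2.1 and 8.4.3.3. Protocol 8.2.2.1 introduces it with "Superiority of aQIV versus aTIV-1 and aTIV-2 for the alternate B strain will be assessed using the GMT ratio" and the SCR difference.

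**Error control.** SAP section 5 sets the level "using a one-sided alpha of 0.025 for each comparison". SAP 8.4 says "No adjustment for multiple comparison and multiplicity will be used", and SAP 11.2.4 says of the secondary analyses "No multiplicity adjustment to the CI levels will be implemented". Neither document contains a gate, a hierarchy or a testing order linking superiority to the co-primary objectives.

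**The concern.** The documents themselves separate descriptive from confirmatory secondary aims. SAP 2.4.2.1 calls the first secondary objective descriptive, and SAP 11.2.2 rules out testing for it. The second has hypotheses and a rule for declaring a result, so it is a second confirmatory claim beside study success.

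Leaving the co-primary endpoints unadjusted is correct, because all of them must be met. That reasoning does not extend to a second claim that can succeed on its own. As written, aQIV can miss a co-primary criterion and still be formally declared superior, and nothing limits the chance that at least one of the two claims is false.

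The unit of the claim is also stated in two ways. The objective and endpoint text (SAP 2.2.1 and 2.2.2; Protocol 8.1.2) uses the word *separately*, and the hypotheses run over k = 1, 2. The declaration rule requires both B strains. If aQIV beat only one aTIV, there could be an argument after unblinding over what may be claimed.

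**Working it through.** **1. Inputs.** One-sided 0.025 per comparison (SAP section 5). The superiority rule uses the upper limit of a two-sided 95% CI, which is also one-sided 0.025 (SAP 2.4.2.1). All co-primary endpoints are required (SAP 2.1.2). Four superiority conditions are required: GMT and SCR for each of two B strains. Stated powers are 82.39% for the eight non-inferiority endpoints and 76.47% for the CBER criteria (SAP Table 5-1).

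**2. The plan's own figures.** The per-strain SCR powers reproduce by normal approximation with the Farrington-Manning null variance: 99.45% for each A strain (800 vs 800) and 91.29% for each B strain (800 vs 400).

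- Four SCR tests: 0.9945² × 0.9129² = 0.8242.
- With the four GMT tests: 0.8242 × 0.9996 = 0.8239.
- CBER titer criterion, B strains: 76.2% (normal) or 75.5% (exact), against 76.47% stated.

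The plan gives no error rate for the two claims together, so there is none to reproduce.

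**3. Each claim alone.** A rule that requires every component to pass has type I error no larger than that of one component. The co-primary claim is therefore at most 0.025, and so is the joint superiority claim.

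**4. The two claims together, no gate.** Worst case: one co-primary null at its boundary, one superiority null at its boundary, and every other condition comfortably met. Then P(at least one false claim) = 0.025 + 0.025 − P(both).

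| Correlation between the two binding statistics | P(both) | P(at least one false claim) |
|---|---|---|
| 0 | 0.0006 | 0.0494 (= 1 − 0.975²) |
| 0.25 | 0.0020 | 0.0480 |
| 0.5 | 0.0046 | 0.0454 |
| 0.75 | 0.0095 | 0.0405 |

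The bound under any dependence is 0.05. The correlations are assumed values; the documents give none.

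**5. Less extreme nulls.** SCR and GMT are computed from the same HI titers, so a strain with no advantage on one would usually have none on the other. If both nulls for one B strain sit at the boundary and the other strain is clearly superior, the false superiority rate is P(both component tests reject): 0.8% at an assumed correlation of 0.7 and 1.1% at 0.8. With one independent co-primary null at its boundary, the two-claim figure is 1 − 0.975 × (1 − 0.0083) = 3.3%, or 1 − 0.975 × (1 − 0.0110) = 3.6%. With all four superiority nulls at the boundary, the false superiority rate in simulation was below 0.1%.

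**6. With a gate.** If any co-primary null is true, a false claim of either kind requires the co-primary set to pass, which has probability at most 0.025. If no co-primary null is true, only the superiority claim can be false, again with probability at most 0.025. The maximum is 0.025 in either case.

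**7. How often the gate would matter.** Multiplying the stated powers as if independent gives 0.8239 × 0.7647 = 63.0%, a 37% chance of missing at least one co-primary endpoint under the design assumptions. If the two B strains are also independent on the titer criterion, 0.8239 × 0.7647² = 48.2%, a 52% chance of a miss. These are power calculations. They show that superiority after a co-primary miss is a plausible outcome, and they say nothing about type I error.

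**The case against.** The strongest reply is that the plan breaks no promise. Its 0.025 is stated per comparison, no family-wise level across primary and secondary objectives is offered, and the absence of adjustment is prespecified. This stands. A reader might infer that the plan fails to hold its own stated alpha, or that a superiority claim after a failed co-primary has no error-rate protection. The documents support neither reading: the joint superiority rule holds 0.025 whether or not the co-primary endpoints pass.

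A reader might also take the 76.47% power as evidence of inflated error. It is not. That figure assumes a true B-strain rate of 64.6%, above the 60% threshold, so missing the criterion would be a false negative.

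A third tempting inference is that there are three claims, which would give 1 − 0.975³ = 7.3% if independent. No decision rule supports this. Every statement of the rule in both documents requires both B strains, and indexing the hypotheses by k is ordinary notation for the components of a joint test. What remains is loose wording that should match the rule.

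Finally, the worst case is contrived, as step 5 shows, and aQIV is expected to beat a vaccine lacking the strain. Superiority also cannot rescue a failed study under SAP 2.4. These points reduce the size of the problem. They do not supply the missing condition.

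**Conclusion.** The point holds as a gap in control across two formal claims. The worst-case chance of at least one false claim is about 4.9% if the claims are independent and about 4.5% at correlation 0.5, against at most 2.5% with a gate. It rests on one binding null at its boundary in each family, all else comfortably met, and normal test statistics with assumed correlations. Realistic inflation is smaller.

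Co-primary type I error is unaffected. The mismatch between the *separately* and k = 1, 2 wording and the joint declaration rule is a second, textual defect that needs aligning whatever view is taken of family-wise error. Label: cheap improvement.

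**What to change.** In SAP 2.4.2.1, 8.4 and 11.2.1, and in Protocol 8.2.2.1 and 8.4.3.3, state that superiority for the alternate B strains is tested, at the same two-sided 95% CI level, only if all co-primary endpoints are met, and that otherwise its confidence intervals are descriptive. State in the same places that superiority is a single joint claim requiring both GMT and SCR for both B strains. Reword the objective and endpoint text (SAP 2.2.1 and 2.2.2; Protocol 2.2 and 8.1.2) and the hypotheses (SAP 11.2.2; Protocol 8.4.3.3.1) to match.

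The cost is wording in two documents before unblinding. SAP section 14 already foresees a protocol update. No alpha, sample size or co-primary power is used. The one loss is that no formal superiority claim could be made if a co-primary endpoint fails, and such a trial is already unsuccessful by its own rule.

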3. STUDY DESIGN

This phase 3 study is a randomized, double-blinded, comparator controlled, parallel-group, multicenter study of aQIV versus the US-licensed 2017-2018 adjuvanted trivalent influenza vaccine (aTIV-1, Fluad), and versus an adjuvanted trivalent influenza vaccine (aTIV-2), containing the alternate B strain. All study vaccine administration will be a single dose, and consistent with the current license for aTIV-1.

The study will be conducted in approximately 1778 male and female adults aged 65 years and older who are healthy or have co-morbidities which increase their risk of complications from influenza infection. Subjects will be randomized to one of the three treatment groups in a 2:1:1 ratio. An Interactive Response Technology (IRT) system will be used for subject randomization.

Subjects will provide serological specimens during the two mandatory clinic visits before and after vaccination on Day 1 and Day 22, respectively, for measurement of immune responses in routine influenza assays. Each subject will complete a Diary Card for solicited local and systemic AEs for 7 days after vaccination. Safety information will also be collected for all unsolicited AEs for 21 days following vaccination; and for the full duration of study participation for serious AEs (SAEs), AEs leading to withdrawal from the study NOCDs, AESIs, and concomitant medications associated with these events. Three scripted safety telephone calls will facilitate the collection of these safety data during the study period, and one reminder phone call will occur during the first few days after vaccination to remind the subject on the completion of the Diary Card.

An unscheduled study visit may be performed at any time during the study to further evaluate safety information described on the telephone.

Any subject who manifests signs of an influenza-like illness (ILI) during the treatment period (Days 1-22) will be evaluated by real time reverse transcription polymerase chain reaction (RT-PCR) testing of a nasopharyngeal (NP) specimen for influenza. Subjects with onset of ILI and RT-PCR-confirmed influenza during the treatment period (Days 1-22) will be removed from the Per Protocol Set (PPS) in the immunogenicity analyses. ILI will also be recorded as an AE.

For further details, please refer to section 3.0 of the protocol.

Table 3-1: Time and Events Table

Assessment	Clinic Visit 1	Reminder Phone Call	Safety Phone Call	Clinic Visit 2	Safety Phone Call	Safety Phone Call¹²
	Day 1	Day 3 (-1 to + 1 days)	Day 15 (-3 to + 3 days)	Day 22 (-3 to + 3 days)	Day 91 (-7 to +7 days)	Day 181 (-14 to +14 days)
EDC Visit no:	1	2	3	4	5	6
Informed consent ¹	✓					
Demographics and influenza vaccination history ^{2,3}	✓					
Medical history and baseline medication use ³	✓					
Physical examination ^{3,4}	✓			✓		
Oral temperature, vital signs, height, weight ³	✓					
Review of eligibility criteria ³	✓					
Blood sample for immunogenicity testing ³	✓			✓		
Vaccination ^{5,6}	✓					
Provision of study supplies and instructions ^{7,8}	✓					
Subject Diary Card reviewed and collected				✓		
Telephone contact ⁹		✓	✓		✓	✓
Assess influenza-like illness (if applicable) ¹⁰	← →					

Assessment	Clinic Visit 1	Reminder Phone Call	Safety Phone Call	Clinic Visit 2	Safety Phone Call	Safety Phone Call¹²
	Day 1	Day 3 (-1 to + 1 days)	Day 15 (-3 to + 3 days)	Day 22 (-3 to + 3 days)	Day 91 (-7 to +7 days)	Day 181 (-14 to + 14 days)
Assess all unsolicited AEs and concomitant medications ¹¹			✓	✓		
Assess SAEs, NOCDs, withdrawal AEs, AESIs & associated medications				↔	↔	

1. The invitation to participate and the informed consent process must be conducted within 10 days before the day of vaccination (Day 1)
2. Confirm that patient has had the opportunity to ask questions and consent form(s) are signed prior to any V118_20 procedures being performed.
3. Procedure to be performed prior to vaccination. All eligibility criteria must be met before any study procedures (eg., blood sampling) can be performed.
4. Physical examination must be performed by a qualified health care practitioner in accordance with local regulations and licensing requirements designated within the Site Responsibility Delegation Log.
5. Vaccination should occur only after the pre-dose blood sample collected.
6. After vaccination, the subject will remain under medical supervision for at least 30 minutes and observed for local and systemic AE and unsolicited AEs. A body temperature measurement (preferably oral) will be taken.
7. A Diary Card, thermometer and ruler will be dispensed at Day 1. Subject will receive instruction on diary completion and thermometer and ruler use.
8. On Day 1 approximately 6 hours after the vaccination or prior to going to bed at the latest, and daily thereafter through Day 7, solicited local and systemic AEs including other AEs (i.e., body temperature measurements and use of analgesics/antipyretics) will be reported daily by the subject in the Diary Card.
9. The reminder call at Day 3 will be made by site staff to remind the subject to complete the Diary Card. In the safety calls at Day 15, Day 91 and day 181, subjects will be interviewed by site staff using a scripted interview for collection of safety data. These safety data will be collected in source documents by the individuals performing the interviews.
10. The subject will be asked to contact the site staff if the subject experiences ILI symptoms^a during the interval between Day 1 and Day 22 (i.e., up to and including the day of the Day 22 blood sample). The subject should visit the site within 3 days of the onset of the ILI in order for a nasopharyngeal swab sample to be taken, however samples will be accepted if collected up to 6 days following the day of ILI onset. The sample will be sent to the central laboratory for RT-PCR analysis.

^a defined as at least one of the following respiratory symptoms: sore throat, cough, sputum production, wheezing, or difficulty breathing; concurrently with at least one of the following systemic symptoms: oral temperature of $>37.2^{\circ}\text{C}/99^{\circ}\text{F}$, chills, tiredness, headache, or myalgia.

11. All AEs through the day 22 visit, and medications used to treat them.
12. Any subject who terminates the study prematurely after receiving a vaccination should have a termination visit/call (Section 5.5.1).

4. RANDOMIZATION AND BLINDING

4.1 Randomization

Enrolled subjects will be randomized in the IRT system and automatically assigned a unique Subject ID. The Subject ID will be the subject's unique identification number for all CRFs and associated study documentation that will be used for duration of the study. After randomization, the Screening Number ceases to be used and remains in the Screening and Enrollment Log only. The list of randomization assignments is produced by the IRT service provider and approved by Seqirus or delegate.

Subjects will be randomized in a 2:1:1 ratio to aQIV, aTIV-1, and aTIV-2.

If for any reason, after signing the informed consent form (ICF), the subject who is eligible and enrolled fails to be randomized, this is called a randomization failure. Further guidance is provided in the CRF Instructions. The reason for all randomization failures should be recorded in the Screening and Enrollment Log and in the source document as specified in the Source Data Agreement (SDA). The information on subjects who are randomization failures should be kept distinct from subjects who are screen failures, as described in Section 5.1.2, Screening of the protocol.

If for any reason, after randomization the subject fails to undergo treatment, this is an Early Termination and the reason should be recorded in source document as specified in the SDA. The information on these Early Termination subjects should be kept distinct in the source documentation from randomization failures.

For further details, please refer to section 5.1.4 of the protocol.

